4.4.2.3 SAEs (including AESIs)

An event will be considered as a serious event if “Yes” is checked for “Serious” in the CRF. An event will be considered as an AESI if “Yes” is checked for “Is the event an AESI?” in the CRF.

SAEs (including AESIs) will be analyzed throughout the study using the following periods:

- Within 7 days (D0 to D7) after vaccination
- Within 30 days (D0 to D30) after vaccination
- During the study (i.e., all SAEs occurred during the study), including the 6-month follow-up period
- During the 6-month follow-up

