4.4.3.3 Subject Duration

The duration of a subject in the study until last visit is computed as follows:

Maximum (Date of last visit, Date of term form) – (Date of V01) +1.

The duration of a subject in the study including follow-up is computed as follows:

Maximum (Date of last visit, Date of term form, Date of last follow-up contact) – (Date of V01) +1.

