5.1.4 Statistical Methods for Observational Objectives

No hypotheses will be tested.

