5.1.4.1 Statistical Methods

Safety

Safety results will be described for subjects in all study groups. The main parameters for the safety endpoints will be described by 95% Cis using the exact binomial method (Clopper-Pearson method) (15).

Safety analyses will contain at least the descriptions listed in [Table 5.5](#):

Table 5.5: Statistical analyses for safety observational objectives

Safety Events	Time and Group	Description
Immediate unsolicited non-serious systemic AE	Within 30 minutes after each vaccination in Group 1 and Group 2	Proportion of subjects that have the event, MedDRA terms, intensity, relationship to vaccine, study discontinuation, duration
Solicited injection site reactions	D0 to D7 after each vaccination in Group 1 and Group 2	Proportion of subjects that have the event, time of onset, duration, intensity, action taken, study discontinuation, number of days of occurrence, temperature collection routes
Solicited systemic reactions		
Unsolicited non-serious AE/AR	D0 to D30 after each vaccination in Group 1 and Group 2	Proportion of subjects that have the event, MedDRA terms, time of onset, duration, intensity, relationship, action taken, study discontinuation
AEs leading to study discontinuation	D0 to D30 after each vaccination in Group 1 and Group 2; D31 to next visit after each vaccination in Group1 and Group2;	Proportion of subjects that have the event, MedDRA terms, time of onset, duration, intensity, relationship,

Safety Events	Time and Group	Description
	During the whole study in Group 1 and Group 2	action taken, study discontinuation
MAAE	D0 to D30 after each vaccination in Group 1 and Group 2; D31 to next visit after each vaccination in Group1 and Group2; During the whole study in Group 1 and Group 2	Proportion of subjects that have the event, MedDRA terms, onset, duration, intensity, relationship, action taken, study discontinuation
SAE (including AESI)	D0 to D7 after each vaccination in Group1 and Group 2; D0 to D30 after each vaccination in Group1 and Group 2; D31 to next visit after each vaccination in Group1 and Group2; During the whole study in Group1 and Group 2	Proportion of subjects that have the event, MedDRA terms, onset, duration, relationship, seriousness criteria, outcome, study discontinuation

Note: “Group1 and Group2” mentioned in the above table 5.5 for safety analyses also includes the Subgroup 1a, Subgroup 1b, Subgroup 2a and Subgroup 2b, when it is applicable.

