5.1.5.2 Subgroup Analysis by Race and Gender

Subgroup analyses by gender and race for will be provided in Appendix 15 of the CSR.

The gender subgroup analyses will have two categories (Female and Male), and the race subgroup analyses will have four categories (White, Black, Asian, and Other).

For primary and secondary immune responses after meningococcal vaccinations, these subgroup analyses will be conducted between Group 1 and Group 2 as well as between Subgroup 1a and 2a by gender and race.

For safety responses, these subgroup analyses will be mostly performed between Group 1 and Group 2 by gender and race.

Immunogenicity analyses

The followings are the serological endpoints will be assessed by gender and race:

- 1) hSBA vaccine seroresponse to meningococcal serogroups A, C, Y, and W assessed before first study vaccination on D0 and 30 days after the 4th meningococcal vaccination (Subgroup 1a vs Subgroup 2a).
- 2) Antibody titers $\geq 1:8$ against meningococcal serogroups A, C, Y, and W measured by hSBA assessed 30 days after vaccinations at 6 months of age (Group 1 vs Group 2).
- 3) The following serological endpoints will be assessed (including effect of 4th dose of MenACYW or Menveo):
 - Before the 12-month vaccination (pre-4th dose) for Subgroups 1a and 2a
 - hSBA meningococcal serogroups A, C, Y and W antibody titers
 - 30 days after the 12-month vaccination for Subgroups 1a and 2a
 - hSBA meningococcal serogroups A, C, Y and W antibody titers
 - Percentage of subjects with titer ≥ 4 -fold rise form pre-dose 4 vaccination to post-dose 4 vaccination and 95%CI
- 4) The following serological endpoints will be assessed (persistence of bactericidal antibodies after infant vaccination with MenACYW or Menveo):
 - 30 days after the 6-month vaccination and before the 12-month vaccination for Subgroup 1a and Subgroup 2a
 - hSBA meningococcal serogroups A, C, Y, and W antibody titers
 - GMTs with 95% CI
 - Percentage of subjects with titer $\geq 1:4$ and $\geq 1:8$ and 95% CI

Safety analyses

Safety overview after any vaccine injection by gender– Overall Safety Analysis Set

Safety overview after vaccine injections at 2 months of age by gender – Safety Analysis Set 1

Safety overview after vaccine injections at 4 months of age by gender – Safety Analysis Set 2

Safety overview after vaccine injections at 6 months of age by gender – Safety Analysis Set 3

Safety overview after vaccine injections at 12 months of age by gender – Safety Analysis Set 4

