5.2.3.1 Overall Safety Analysis Set for Any Dose

The overall SafAS is defined as those subjects who have received at least one dose of the study vaccines and have any safety data available. All subjects will have their safety analyzed after any dose according to the vaccine received at the first dose.

Safety data recorded for a vaccine received out of the protocol design will be excluded from the analysis (and listed separately).

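### Whole-study safety percentages for Group 1 and Group 2 rest on unequal planned follow-up, and the SAP does not guarantee the subgroup columns that would show it (minor)

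*SAP*

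**What the plan says.** SAP 5.1.4.1, Table 5.5, gives the proportion of subjects with AEs leading to discontinuation, MAAEs and SAEs/AESIs over several windows, the last of them "During the whole study in Group 1 and Group 2". For SAEs, SAP 4.4.2.3 defines this period as "During the study (i.e., all SAEs occurred during the study), including the 6-month follow-up period". The note under Table 5.5 says that the two group labels "also includes the Subgroup 1a, Subgroup 1b, Subgroup 2a and Subgroup 2b, when it is applicable". It does not say which rows or tables that covers.

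For the overall safety set, SAP 5.2.3.1 says "All subjects will have their safety analyzed after any dose according to the vaccine received at the first dose". In the complementary outputs, SAP 5.1.5.2 says "For safety responses, these subgroup analyses will be mostly performed between Group 1 and Group 2 by gender and race"; one of the listed outputs is "Safety overview after any vaccine injection by gender".

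Two provisions touch follow-up. SAP 4.4.3.3 has a derivation introduced by "The duration of a subject in the study including follow-up is computed as follows", and SAP Table 5.1 plans generic descriptive statistics for baseline characteristics and follow-up. On inference, SAP 5.1.4 says "No hypotheses will be tested".

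The design is in the Protocol Synopsis and the Tables of Study Procedures. Subgroup 1a has 6 visits, 4 of them vaccination visits, over 16-19 months. Subgroup 1b has 7 visits, 2a has 8 and 2b has 7; each has 5 vaccination visits over 19-22 months. Every child is to receive 4 meningococcal doses.

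**The concern.** A crude proportion over the whole study counts children with at least one event in whatever time they were observed. Two-thirds of Group 1 is planned to be observed for about 3 months less than every child in Group 2. If both vaccines had the same safety profile, and families attended at similar points in their windows, the MenACYW column would still tend to show lower whole-study percentages. A table built with only the two pooled columns would comply with the SAP and would not show the reader why.

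The same reasoning applies to any overview after any dose that pools 1a with 1b, because 1a has one study vaccination visit fewer. What is at stake is how a descriptive table is read. The imbalance leans towards the investigational vaccine, in a trial whose observational objective is to describe the safety of both products.

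**Working it through.** **1. The plan's own figures reproduce.** 2628 × 2/3 = 1752 and 2628 / 3 = 876. A further 2:1 split gives 1168 / 584 in Group 1 and 584 / 292 in Group 2. Age at last contact (18-21 months in 1a, 21-24 elsewhere) minus 2 months gives 16-19 and 19-22 months.

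**2. Planned exposure.** Mean follow-up at the midpoints (17.5 and 20.5 months):
- Group 1: (1168 × 17.5 + 584 × 20.5) / 1752 = 18.5 months. Group 2: 20.5 months. Ratio 0.90.
- Short end: (2 × 16 + 19) / 3 = 17 vs 19 (0.89). Long end: (2 × 19 + 22) / 3 = 20 vs 22 (0.91).
- Opposite extremes: 17 / 22 = 0.77 and 20 / 19 = 1.05, so the direction can reverse if the groups attend very differently.
- Vaccination visits: (2 × 4 + 5) / 3 = 4.33 vs 5.

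**3. Whole-study shift with no true difference.** The documents give no event rates for this trial, so the Group 2 risk P and the shape of the hazard are assumptions. Take h(t) = h0 × 2^(-t/L), with h0 solved so that risk at 20.5 months is P. Then Group 1 = (2 × risk at 17.5 months + P) / 3. The half-width is 1.96 × sqrt(P(1 - P)(1/1752 + 1/876)).

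| Group 2 risk | Constant hazard | Halving every 12 months | Halving every 6 months | 95% half-width of the difference |
|---|---|---|---|---|
| 5% | 4.52% (-0.5) | 4.73% (-0.3) | 4.86% (-0.1) | 1.8 |
| 20% | 18.23% (-1.8) | 19.00% (-1.0) | 19.49% (-0.5) | 3.2 |
| 50% | 46.44% (-3.6) | 48.02% (-2.0) | 49.00% (-1.0) | 4.1 |

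Entries are the Group 1 percentage, with the shift in points in brackets. The shift reaches the half-width only for very common events under a constant hazard: at 70%, Group 1 is 66.15%, a shift of 3.9 points against a half-width of 3.7.

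**4. Any-dose shift, if 1a and 1b are pooled.** With equal, independent risk per visit, q = 1 - (1 - P)^(1/5), the 1a risk is 1 - (1 - q)^4, and Group 1 = (2 × 1a risk + P) / 3. At P = 50%, q = 0.129, 1a = 42.6% and Group 1 = 45.0%, a shift of 5.0 points. The shift is 0.7 points at 5%, 2.7 at 95% and 1.0 at 99%. With an assumed within-child correlation (beta-binomial), the 5.0 points at 50% fall to 3.3 (correlation 0.2) or 1.9 (0.5).

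**5. Would a person-month rate repair it?** Only under a constant hazard. With no true difference and a hazard halving every 6 months, the Group 1 / Group 2 first-event rate ratio is 1.06 at 50% risk and 1.08 at 5%, now tilted the other way.

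**6. A time that every subgroup reaches.** The shortest planned follow-up in 1a is for a child enrolled at 89 days, given Visit 5 on turning 12 months and called 180 days later: 365 - 89 + 180 = 456 days (15.0 months). For 1b and Group 2, with the last vaccination at 15 months of age, it is 456 - 89 + 180 = 547 days (18.0 months).

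**7. Precision of 1b vs Group 2.** 1.96 × sqrt(P(1 - P)(1/584 + 1/876)) gives 2.3 points at 5% and 5.2 at 50%, against 1.8 and 4.1 for the pooled contrast.

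**The case against.** The strongest reply is that the SAP already foresees subgroup columns. The subgroups differ only from the second year, so whole-study rows are an obvious place for the note to apply, and Table 5.5 is stated as a minimum. This stands in part: a reader might infer that the plan commits to two pooled columns, and it does not. But the condition is undefined, so the subgroup columns are not guaranteed either.

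Second, follow-up is not ignored. A reader might infer that no summary of it is planned. SAP 4.4.3.3 derives the duration and Table 5.1 plans a generic description. What is missing is a stated display by group and subgroup beside these rows.

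Third, the layout of the main any-dose tables is not in the documents. The any-dose overviews listed are those by gender, race and preterm status, and 5.2.3.1 fixes how children are assigned to a vaccine, not which columns are printed. The any-dose figures above are therefore conditional on pooling.

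Fourth, the lower visit count matters less than it seems for SAEs and MAAEs. Children in 1a receive the 15-18 month Pentacel dose from study staff outside the study, and their SAE/MAAE collection runs to 180 (+30) days after Visit 5, at about 18-21 months of age. Events after that dose can still be captured. This stands; duration is the main issue for the whole-study rows.

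Fifth, safety is descriptive, the fixed windows after each dose, the visit-specific sets SafAS1 to SafAS5 and the 6-month follow-up period are unaffected, and the event rates are assumed. All of this stands and sets the severity.

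**Conclusion.** The point holds as a minor, cheap improvement. The difference in planned follow-up is a fact of the design (18.5 vs 20.5 months at the midpoints), and the SAP does not ensure that the whole-study rows reveal it. With like attendance and equal true safety, the pooled Group 1 percentages lean low by about 0.1-0.5 points at 5% risk and 1.0-3.6 at 50%, depending on an assumed hazard shape. Both lie inside sampling error. A pooled any-dose overview could lean by up to about 5 points at 50%, beyond the 4.1-point half-width, but only if visits are independent.

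Two stronger readings are not supported. The documents do not show that any safety or immunogenicity conclusion would change: no safety hypothesis is tested, and the primary objectives do not use these tables. Nor is Subgroup 1b vs Group 2 a fully matched comparison. Vaccination visits and planned duration agree, but 2a (584 of the 876 in Group 2) has 8 visits against 7 in 1b. At Visit 5, 1b receives three vaccines and Group 2 four; at 15-18 months, 1b receives three and Group 2 two. The 4th meningococcal dose is at 15-18 months in 1b and at 12 months in Group 2.

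**What to change.** 1. In SAP Table 5.5, state that the whole-study rows always show 1a and 1b separately beside the pooled columns, and apply the same rule to any any-dose overview.
2. Beside those rows, print the duration including follow-up from SAP 4.4.3.3 by group and subgroup.
3. Add Kaplan-Meier cumulative incidence of SAEs/AESIs and of MAAEs at 456 days from Visit 1, censoring at the derived duration. State that this equalises follow-up time but not vaccination visits: a Group 2 child enrolled at 42 days is 498 days old at that point and may already have had the fifth vaccination visit.
4. Present 1b vs Group 2 as a supportive contrast with equal numbers of vaccination visits and equal planned duration, listing the differences in total visits, vaccines per visit and age at the 4th meningococcal dose.
5. If a person-time rate is added, state its constant-hazard assumption.

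Keep the pooled rows, since the 456-day figure leaves out later events. The cost is SAP wording and a few tables from dates already collected. The supportive contrast sets aside two-thirds of MenACYW recipients and is less precise (half-width about 5.2 vs 4.1 points at 50%).

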5.1.5 Complementary Output

5.1.5.1 Sensitivity Analysis due to Blood Sample Issues

If applicable and necessary, additional immunogenicity sensitivity analyses will be performed for subjects with blood samples handled incorrectly during collection, processing, storage or shipment, and may have potential impact on the analysis results (eg, blood samples stored out of temperature after a power outage) based on the PPASs. The outputs will be provided in Appendix 15 of the CSR.

The endpoint for the sensitivity analyses will be the GMT.

- hSBA GMTs and 95% CI at each time point for each group by blood sample status – Per-Protocol Analysis Set 1
- hSBA GMTs and 95% CI at each time point for each group by blood sample status – Per-Protocol Analysis Set 2
- hSBA GMTs and 95% CI at each time point for each group by blood sample status – Per-Protocol Analysis Set 3

5.1.5.2 Subgroup Analysis by Race and Gender

Subgroup analyses by gender and race for will be provided in Appendix 15 of the CSR.

The gender subgroup analyses will have two categories (Female and Male), and the race subgroup analyses will have four categories (White, Black, Asian, and Other).

For primary and secondary immune responses after meningococcal vaccinations, these subgroup analyses will be conducted between Group 1 and Group 2 as well as between Subgroup 1a and 2a by gender and race.

For safety responses, these subgroup analyses will be mostly performed between Group 1 and Group 2 by gender and race.

Immunogenicity analyses

The followings are the serological endpoints will be assessed by gender and race:

- 1) hSBA vaccine seroresponse to meningococcal serogroups A, C, Y, and W assessed before first study vaccination on D0 and 30 days after the 4th meningococcal vaccination (Subgroup 1a vs Subgroup 2a).
- 2) Antibody titers $\geq 1:8$ against meningococcal serogroups A, C, Y, and W measured by hSBA assessed 30 days after vaccinations at 6 months of age (Group 1 vs Group 2).
- 3) The following serological endpoints will be assessed (including effect of 4th dose of MenACYW or Menveo):
 - Before the 12-month vaccination (pre-4th dose) for Subgroups 1a and 2a
 - hSBA meningococcal serogroups A, C, Y and W antibody titers
 - 30 days after the 12-month vaccination for Subgroups 1a and 2a
 - hSBA meningococcal serogroups A, C, Y and W antibody titers
 - Percentage of subjects with titer ≥ 4 -fold rise form pre-dose 4 vaccination to post-dose 4 vaccination and 95%CI
- 4) The following serological endpoints will be assessed (persistence of bactericidal antibodies after infant vaccination with MenACYW or Menveo):
 - 30 days after the 6-month vaccination and before the 12-month vaccination for Subgroup 1a and Subgroup 2a
 - hSBA meningococcal serogroups A, C, Y, and W antibody titers
 - GMTs with 95% CI
 - Percentage of subjects with titer $\geq 1:4$ and $\geq 1:8$ and 95% CI

Safety analyses

Safety overview after any vaccine injection by gender– Overall Safety Analysis Set

Safety overview after vaccine injections at 2 months of age by gender – Safety Analysis Set 1

Safety overview after vaccine injections at 4 months of age by gender – Safety Analysis Set 2

Safety overview after vaccine injections at 6 months of age by gender – Safety Analysis Set 3

Safety overview after vaccine injections at 12 months of age by gender – Safety Analysis Set 4

Safety overview after vaccine injections at 15 months of age by gender – Safety Analysis Set 5

Safety overview after vaccine injections by gender –Safety Analysis Set for All 4-Dose Vaccination

Vaccination

Safety overview after any vaccine injection by race – Overall Safety Analysis Set

Safety overview after vaccine injections at 2 months of age by race – Safety Analysis Set 1

Safety overview after vaccine injections at 4 months of age by race – Safety Analysis Set 2

Safety overview after vaccine injections at 6 months of age by race – Safety Analysis Set 3

Safety overview after vaccine injections at 12 months of age by race – Safety Analysis Set 4

Safety overview after vaccine injections at 15 months of age by race – Safety Analysis Set 5

Safety overview after vaccine injections by race – Safety Analysis Set for All 4-Dose Vaccination

5.1.5.3 Subgroup Analyses by Preterm and Full-term Birth

Subgroup analyses by preterm (gestational age < 37 weeks) and full-term birth (gestational age \geq 37 weeks) between Group 1 and Group 2 including Subgroup 1a, Subgroup 1b and Subgroup 2a will be provided in Appendix 15 of the CSR.

Immunogenicity analyses

The following serological endpoints will be assessed:

- D0 (before first vaccination) for Group 1 and Group 2 by preterm and full-term birth:
 - hSBA meningococcal serogroups A, C, Y and W antibody titers
- 30 days after the 6-month vaccination (after the 3rd dose) for Group 1 and Group 2 by preterm and full-term birth:
 - hSBA meningococcal serogroups A, C, Y, and W antibody titers
 - Titer distribution and reverse cumulative distribution curves (RCDCs)
 - hSBA meningococcal serogroups A, C, Y, and W antibody titers \geq 1:4 and \geq 1:8
 - hSBA meningococcal serogroups A, C, Y, and W antibody titers \geq 4-fold rise from pre-vaccination (D0) to post-3rd vaccination
 - hSBA vaccine seroresponse
- D0 before first vaccination for Subgroup 1a, Subgroup 1b and Subgroup 2a (G1a vs G2a and G1a vs G1b) by preterm and full-term birth:
 - hSBA meningococcal serogroups A, C, Y, and W antibody titers
- 30 days after the 12-month vaccinations for Subgroup 1a and Subgroup 2a, after the 15-month vaccinations for Subgroup 1b (G1a vs G2a and G1a vs G1b) by preterm and full-term birth:
 - hSBA meningococcal serogroups A, C, Y, and W antibody titers
 - Titer distribution and RCDCs
 - hSBA meningococcal serogroups A, C, Y, and W antibody titers \geq 1:4 and \geq 1:8
 - hSBA meningococcal serogroups A, C, Y, and W antibody titers \geq 4-fold rise from pre-vaccination (D0) to post-dose 4 vaccination
 - hSBA vaccine seroresponse
- 30 days after the 3rd dose (after 6-month vaccination) and before the 4th dose of MenACYW conjugate vaccine or MENVEO® (before 12-month vaccination for Subgroup 2a and Subgroup 1a, before 15-month vaccination for Subgroup 1b) to evaluate the immune persistence (G1a vs G2a and G1a vs G1b) by preterm and full-term birth:
 - hSBA meningococcal serogroups A, C, Y, and W antibody titers
 - hSBA meningococcal serogroups A, C, Y, and W antibody titers \geq 1:4 and \geq 1:8
- 30 days after the 4th dose (after 12-month vaccination for Subgroup 1a and Subgroup 2a, after 15-month vaccination for Subgroup 1b) of MenACYW conjugate vaccine or MENVEO® during 2nd year of life vaccination, including evaluating the effect of the 4th dose (G1a vs G2a and G1a vs G1b) by pre-term and full-term birth:
 - hSBA meningococcal serogroups A, C, Y, and W antibody titers
 - hSBA meningococcal serogroups A, C, Y, and W antibody titers \geq 1:4 and \geq 1:8
 - hSBA meningococcal serogroups A, C, Y, and W antibody titers \geq 4-fold rise from pre-4th dose vaccination to post-4th dose vaccination
 - hSBA vaccine seroresponse

Safety analyses

Safety overview after any vaccine injection by the preterm and full-term birth – Overall Safety Analysis Set

Safety overview after vaccine injections at 2 months of age by the preterm and full-term birth – Safety Analysis Set 1

Safety overview after vaccine injections at 4 months of age by the preterm and full-term birth – Safety Analysis Set 2

Safety overview after vaccine injections at 6 months of age by the preterm and full-term birth – Safety Analysis Set 3

Safety overview after vaccine injections at 12 months of age by the preterm and full-term birth – Safety Analysis Set 4

Safety overview after vaccine injections at 15 months of age by the preterm and full-term birth – Safety Analysis Set 5

Safety overview after vaccine injections by the preterm and full-term birth –Safety Analysis Set for All 4-Dose Vaccination

Summary of unsolicited AEs within 30 days after vaccine injections by preterm and full-term birth - Overall Safety Analysis Set for Any Dose

Sensitivity Analysis due to COVID-19 Pandemic

The impact of COVID-19 pandemic situation on study conduction will be summarized through impact on visit procedures, study completion and major/critical protocol deviations due to COVID-19.

The subjects impacted by COVID-19 pandemic situation will be defined as the subjects with at least one major/critical protocol deviation due to COVID-19 or who did not complete the study due to COVID-19 or who reported a 6-month follow up not completed in pandemic form. If more than 10% of subjects are impacted as per this definition, baseline and demographics characteristics, and the main immunogenicity and safety endpoints will also be summarized in the subsets of subjects impacted/ non-impacted subjects to assess the potential impact of COVID-19 situation on study outcome.

The assessment of the impact COVID-19 pandemic will be based on but not limited to the following analysis:

- To summarize the impact of COVID-19 on the overall study conduct
 - Early termination due to COVID-19
 - Impact on visit conduct (visit not done, partially done, data collection method/procedure change)
 - Major and critical protocol deviations due to COVID-19
- To summarize disposition across study visits for subjects impacted/not impacted by COVID-19
- To summarize baseline demographics by randomized group for subjects impacted /not impacted by COVID-19
- To provide an individual listing of subjects impacted by COVID-19 and how they were impacted

- To provide a listing of visits impacted by COVID-19 and how they were impacted
- To assess the potential impact of COVID-19 on the main immunogenicity and safety endpoints in the subsets of impacted/non-impacted subjects

